4.8.5.2 Electrocardiogram

Summary displays for ECG parameters (heart rate, PR mean, RR interval, QRS duration, duration, QT interval, QTcB interval, and QTcF interval) will be produced. ECG parameters should be performed 3 hours +/- 1 hour after the drug administration per protocol. Two separate summaries will be produced: one excluding results for ECGs performed outside that window and one including all results regardless of whether the

results were obtained within that window. Summary statistics of observed and change from baseline values will be tabulated by visit and treatment group.

If there are multiple records of ECG measurements at any post-baseline visit, the worst result will be used. Missing data will be maintained as missing.

4.8.5.3 Physical and Neurological Examinations

Results of physical examination at each visit will be summarized by body system, treatment group, and visit. Physical examination results will also be listed.

Treatment-emergent abnormal findings are the values which are normal at baseline and fall into the abnormal categories post-baseline. This will also include values which are abnormal post-baseline, but have no baseline value. The number and percentage of subjects experiencing a treatment-emergent abnormal physical examination finding, by body system and treatment group will be summarized.

Results of a general neurological exam will also be summarized for each parameter in each module by treatment group and visit. The general neurological exam can be found in Appendix 7 of the protocol. Neurological examination results will also be listed.

4.8.5.4 Columbia Suicide Severity Rating Scale

The results of the C-SSRS will be summarized using number of subjects and percentages with (i) events in suicidal behavior, (ii) suicidal ideation, and (iii) suicidal behavior and ideation.

Suicidal ideation is defined as an event in any of the following 4 categories:

- Wish to be dead (Q1)
- Non-specific active suicidal thoughts (Q2)
- Active suicidal ideation with any methods (not plan) without intent to act (Q3)
- Active suicidal ideation with some intent to act, without specific plan (Q4)
- Active suicidal ideation with specific plan and intent (Q5)

Suicidal behavior is defined as an event in any of the following categories:

- Actual attempt
- Interrupted attempt
- Aborted attempt
- Preparatory acts or behavior

- Suicidal Behavior
- Complete Suicide

Complete suicide is not supplied for the lifetime questionnaire but is supplied only for the previous 6 months.

The incidence of subjects with suicidal behavior and self-injurious behavior will be summarized by treatment group and visit. A by-subject listing of the C-SSRS questionnaire data will be provided.

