7.2.1 Screening (Visit 1, Day -28 to -14)

The screening visit (visit 1) will take place 14 to 28 days before the baseline visit. The following procedures will be performed:

- Obtain written informed consent;
- Inclusion/exclusion criteria review including
 - Demographics
 - NINCDS-ADRDA criteria
 - MMSE
 - C-SDD
 - MHIS
 - MRI or CT scan if not performed with the past 12 months
 - Medical history
 - Prior and concomitant treatment review
 - C-SSRS (screening version)
- AE review
- Physical and neurological examinations
- Blood pressure measurement
- ECG
- Blood and urine samples for clinical laboratory tests, including pregnancy test for women of childbearing potential
- Plasma sample for measurement of donepezil and memantine levels.
- ADAS-Cog

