7.2.2 Baseline Visit (Visit 2, Day 1)

The following procedures will be performed at the baseline visit on Day 1 of the study:

- Inclusion/exclusion criteria review
- Medical history
- AE review
- Concomitant medications review

- Physical and neurological examinations
- Blood pressure measurement
- MMSE
- ADAS-Cog
- CDR-SB, ADCS-ADL, NPI and C-SDD
- C-SSRS (since last visit version)
- ECG
- Blood and urine samples for clinical laboratory tests
- Blood sample for APO-E genotype testing
- Study drug dispensation

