8.6.6 Additional Safety Assessments

A by-subject C-SSRS data listing will be provided.

Change from baseline in C-SSRS scores will be summarized by visit and differences between each SUVN-502 dose group (50 mg and 100 mg) and placebo will be reported for Weeks 4, 13 and 26.

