4.2.1 General Definitions

Unless otherwise stated, baseline measurement is defined as the latest, valid pre-dose assessment available. 'End of Study' is defined as the last available post-treatment assessment. A subject who completes all study visits up to Week 30, will be considered to have completed the study. For evaluation of efficacy, a completed subject is defined as any subject who completes all visits up to Week 26.

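### C-SSRS look-back runs from 14–28 days at baseline to 91 days at Week 26, so by-visit incidence and change from baseline cannot be read as a time trend

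*SAP*

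**What the plan says.** **Forms.** Protocol 7.2.1 assigns the screening version of the C-SSRS to the screening visit. Protocol 7.2.2 to 7.2.6 assign the since-last-visit version to Day 1 and to Weeks 4, 13, 26 and 30. Appendix 8 prints both. The screening form asks about the past 2 months for ideation and the past 6 months for behavior.

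**By-visit display.** SAP 4.8.5.4: "The incidence of subjects with suicidal behavior and self-injurious behavior will be summarized by treatment group and visit". This sentence covers behavior and self-injury, not ideation. The same section opens with a broader summary, "The results of the C-SSRS will be summarized using number of subjects and percentages with (i) events in suicidal behavior, (ii) suicidal ideation" and the two combined, for which it names neither a visit nor a period.

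**Change from baseline.** Protocol 8.6.6: "Change from baseline in C-SSRS scores will be summarized by visit and differences between each SUVN-502 dose group" and placebo are to be reported for Weeks 4, 13 and 26. SAP 4.8.5.4 neither repeats this analysis nor withdraws it.

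**Baseline.** SAP 4.2.1: "baseline measurement is defined as the latest, valid pre-dose assessment available". Protocol 8.2 has the same rule.

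**Early termination.** SAP 4.2.2 assigns assessments at an early withdrawal visit to the closest scheduled visit.

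**Form names.** SAP 4.8.5.4 also says: "Complete suicide is not supplied for the lifetime questionnaire but is supplied only for the previous 6 months".

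Neither document gives the look-back in days, adjusts any C-SSRS summary for it, or warns against reading across visits.

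**The concern.** A since-last-visit form counts whatever happened between two visits. When the gaps are unequal, the percentage positive depends on the length of the gap as well as on the underlying rate. Side by side, the by-visit rows invite the reading that suicidality climbs during treatment and recedes in washout. That is how a drug signal would look, and it can arise with no change in rate at all. Change from baseline has the same problem, because its reference is the Day 1 form, which has the shortest or nearly the shortest window.

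The baseline rule adds a second difficulty. It selects the Day 1 form and leaves out the screening form with its longer recall. Exclusion 18 in Protocol 4.2 bars recent ideation at Items 4 or 5 and recent behavior, but does not automatically bar Items 1 to 3. A subject can report ideation without intent at screening, be negative on the short Day 1 form, and enter the analysis with a clean reference.

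Suicidality is part of a named safety objective (Protocol 2.2, SAP 2), so its display should not need mental correction by the reader.

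**Working it through.** The plan states no C-SSRS rate or precision, so there is no figure of its own to reproduce. The windows come from the visit schedule; the event rate is an assumption, shown over a range.

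**Step 1: look-back windows.** Each is the scheduled day minus the previous scheduled day. Ranges use the visit tolerances in Protocol 7.1.

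- Baseline: 14 to 28 days after screening.
- Week 4: 28 − 1 = 27 days (25–29).
- Week 13: 91 − 28 = 63 days (59–67).
- Week 26: 182 − 91 = 91 days (86–96).
- Week 30: 210 − 182 = 28 days (23–33).

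The Week 26 window is 91/28 = 3.25 to 91/14 = 6.5 times the baseline window.

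**Step 2: expected percentage positive under a constant rate.** Let r be the assumed 28-day incidence. Then λ = −ln(1 − r)/28 per day, and the expected proportion over d days is 1 − exp(−λd). For r = 1%, λ = 0.01005/28 = 0.000359; over 91 days the result is 1 − exp(−0.0327) = 3.21%.

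| Visit | Days | r = 0.5% | r = 1% | r = 2% | r = 5% |
|---|---|---|---|---|---|
| Baseline | 14–28 | 0.25–0.50 | 0.50–1.00 | 1.01–2.00 | 2.53–5.00 |
| Week 4 | 27 | 0.48 | 0.96 | 1.93 | 4.83 |
| Week 13 | 63 | 1.12 | 2.24 | 4.44 | 10.90 |
| Week 26 | 91 | 1.62 | 3.21 | 6.35 | 15.35 |
| Week 30 | 28 | 0.50 | 1.00 | 2.00 | 5.00 |

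Across these rates, Week 26 over baseline is 6.5 to 6.1 with a 14-day baseline window and 3.2 to 3.1 with a 28-day window. Week 26 over Week 4 is 3.4 to 3.2. Week 30 over Week 26 is 0.31 to 0.33. The ratios hardly depend on r. In an arm of 179 with full attendance and r = 1%, the expected counts are 0.9–1.8 at baseline, 1.7, 4.0 and 5.8 at Weeks 4, 13 and 26, and 1.8 at Week 30.

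**Step 3: windows that leave the schedule.** An early termination visit on Day 150, as an example, is 59 days from Week 13 and 32 from Week 26. It therefore joins the Week 26 row with a look-back of 150 − 91 = 59 days instead of 91. A subject who misses Week 13 has a Week 26 look-back of 182 − 28 = 154 days. So the window also varies between subjects within a row.

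**Step 4: what the reference covers.** Under the baseline rule it covers 14–28 days. With the screening form added (2 months taken as 61 days, 6 months as 183), it would cover 61 + 14 = 75 to 61 + 28 = 89 days for ideation, and 183 + 14 = 197 to 183 + 28 = 211 days for behavior.

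**The case against.** The strongest reply is that the comparison that matters is between arms, and all arms share the schedule. That stands: a same-visit contrast with placebo is not biased by the scheduled windows. Only the off-schedule windows of Step 3 could differ by arm, and only if early termination or missed visits do. Safety is also read descriptively, without formal testing (SAP 4.7.1.3).

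Four stronger readings are tempting, and the documents do not support them.

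- **That suicidality must rise over the study by construction.** The rise is an expectation under a constant rate, confined to the treatment visits; the window returns to 28 days at Week 30. Protocol 4.3 and 6.2.6.1 also remove some positive subjects from later visits, which works against a rise.
- **That this is the only suicidality display.** Protocol 6.2.6.1 requires all such reports to be recorded as adverse events. They then enter the treatment-emergent tables (SAP 4.8.2), which count new or worsened events by arm regardless of visit windows. A by-subject C-SSRS listing is also planned. The adverse event tables do not replace a C-SSRS summary, since they rest on coded event reports and their treatment-emergent definition sets no end at Week 26.
- **That the SAP counts recurrent pre-study ideation as new.** It defines no new-onset C-SSRS category and nets nothing against baseline. The gap in the reference affects the protocol's change analysis and any new-event count added later.
- **That the percentages above describe the SAP's by-visit table.** That table covers behavior and self-injury. Given exclusion 18, its counts may be very small, whatever the ratio between visits.

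It can also be argued that the SAP governs and has simply dropped change from baseline. SAP 4.2 does say all summaries follow the SAP, but nothing states that the protocol's analysis was withdrawn, so its status should be settled.

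**Conclusion.** The point holds as a matter of display and reference, not as a bias in the treatment comparison. By-visit C-SSRS incidence and change from baseline by visit are not comparable across visits within an arm. With a constant rate, expected incidence at Week 26 is about 3 to 6.5 times that at baseline, then falls to about a third of the Week 26 level at Week 30.

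The window lengths come directly from the schedule. The multiples assume independent events at one common, constant rate and no selective loss of positive subjects. If positives are concentrated in a few subjects with persistent ideation, or positive subjects are withdrawn, the multiple is smaller. The absolute percentages depend on a rate the documents do not give.

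Omitting the screening form from the reference is certain under the baseline rule as written. How many enrolled subjects it affects cannot be known from the documents. The better summary uses data already collected, which is the main reason to make the change.

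**What to change.** In SAP 4.8.5.4, with Protocol 8.6.6 brought into line:

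1. Define the pre-treatment C-SSRS reference as the worst response over the screening and baseline forms, as an explicit exception to the general baseline rule.
2. Replace change from baseline by visit with the number and percentage of subjects per arm who have any, and who have new or worsened, ideation or behavior over the double-blind period. Add an exposure-adjusted rate, such as subjects with an event per 100 subject-years. Show Week 30 separately. The ideation reference (75–89 days) remains shorter than the double-blind period (27 + 63 + 91 = 181 days), so new events should be compared with placebo and not read against zero.
3. If by-visit rows are kept, print the look-back days beside each visit and state that rows are not to be compared across visits.

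Separately, as a clerical matter, correct the sentence on the lifetime questionnaire. Appendix 8 contains only the screening and since-last-visit forms, and its completed-suicide item appears only on the latter. The same SAP section announces four ideation categories and lists five.

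The cost is some wording and one table shell, with no new data. The downside is that the by-visit change display is demoted.

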4.8.6 Safety Monitoring (Data and Safety Monitoring Board [DSMB])

A DSMB will be assembled to periodically review and evaluate accumulated study data for subject safety, study conduct and progress. The DSMB will have the responsibility to make recommendations concerning the continuation, modification, or termination of the study based on their independent evaluation of all study related safety data. The DSMB will consist of a chairperson and at least 2 additional members, including 1 statistician. The approved DSMB charter enumerates the roles of the DSMB members, the frequency with which it meets, and the structure of their meetings. A separate SAP for analyses associated with the DSMB lists out the specific analyses that the DSMB will review.

4.9 Other Analyses

4.9.1 Pharmacokinetics Analyses

Concentration data (trough levels) will be summarized for SUVN-502 and M1 of SUVN-502 for each visit by treatment group.

Concentration data for donepezil and memantine (trough levels) will be summarized for each visit by treatment group.

Summaries will include the geometric mean, arithmetic mean, minimum, maximum, SD, and % coefficient of variation (CV). The summaries will be based on the SP.

Concentration data for SUVN-502 and M1 of SUVN-502 as well as donepezil and memantine will be excluded from the analyses if the sample of blood was drawn after the subject received the daily dose of the particular medication.

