1.1.3 Summary of Findings from Previous Clinical Studies

[figure not shown]
Two phase 1 clinical studies enrolled 122 healthy subjects, including 104 who received SUVN-502 at single oral doses of 5 to 200 mg or daily oral doses of 50 to 130 mg during 7 to 14 days:

- In the First-in-Human study, SUVN-502 was tested at single doses up to 200 mg/day and repeated doses up to 130 mg/day for 7 days; the drug was well tolerated. This study was conducted using a capsule formulation.
- The second phase 1 study used the immediate release (IR) tablet formulation. SUVN-502 was well tolerated at both 50 mg and 100 mg administered as a single dose in healthy elderly male, young adult male or female subjects or as repeated daily doses in healthy elderly male subjects. No safety concerns or notable differences between age, gender, and food groups were reported based on safety laboratory, vital signs, electrocardiograms (ECGs), and physical examination assessments. No safety concerns or notable differences between SUVN-502 50 mg, SUVN-502 100 mg, or active-treated cohorts and placebo were reported based on safety laboratory, vital signs, ECG, physical examination, and C-SSRS assessments.

After a single oral dose of 100 mg, there was no significant effect of gender and food on the pharmacokinetics of SUVN-502 and M1 of SUVN-502.

Following repeated daily doses of SUVN-502, steady state was reached for SUVN-502 on Day 4 and Day 2 for the 50 mg and 100 mg dose groups, respectively. For metabolite M1 of SUVN-502, steady state was reached on Day 6 and Day 4 for the 50 mg and 100 mg dose groups, respectively. After daily doses of SUVN-502 50 mg, SUVN-502 exposure was approximately 1.5 to 1.6-fold higher on Day 14 compared to Day 1, while metabolite M1 of SUVN-502 exposure was approximately 2.1 to 2.5-fold higher on Day 14 compared to Day 1. After daily doses of SUVN-502 100 mg, SUVN-502 exposure was comparable between Day 14 and Day 1, while metabolite M1 of SUVN-502 exposure was approximately 1.6 to 1.8-fold higher on Day 14 compared to Day 1. On Day 14, median time to maximum concentration (t_{max}) of SUVN-502 was 2.00 and 2.98 hours after daily doses of 50 mg and 100 mg respectively. Mean half-life was comparable between the two doses at 13.7 and 12.5 hours, respectively. Median t_{max} of metabolite M1 of SUVN-502 and absorption lag time were similar between the two doses at 3.0 hours and 0 hours, respectively.

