Blinded SUVN-502/placebo treatment and generic formulations of donepezil HCl 10 mg and memantine HCl 10 mg will be dispensed to the subjects for treatment until the next visit.

During the 26-week treatment period, subjects and caregivers will have study visits at Weeks 4, 13, and 26. At each of these visits, subjects will be evaluated for AEs and undergo physical and neurological examination, blood pressure assessment, and ECG. The MMSE, ADAS-Cog, CDR-SB, ADCS-ADL, NPI, C-SDD and C-SSRS scores will be assessed. Urine and blood samples for laboratory evaluations will be collected at Weeks 4 (liver function tests only), 13 and 26. For women of childbearing potential, a pregnancy test will be performed at Week 26. Blood samples for plasma levels of SUVN-502, its metabolite (M1 of SUVN-502), donepezil and memantine will be collected at Weeks 4 and 26.

Subjects who complete the 26-week treatment period, will undergo a 4-week single-blind placebo washout period. At Week 30, subjects will attend a follow-up visit to the study center. During this visit, subjects will be evaluated for AEs and undergo physical and neurological examination, blood pressure assessment, ECG, laboratory evaluations. The C-SDD and C-SSRS scores will be assessed.

Subjects who discontinue treatment prematurely (see Section 4.3) should attend a final visit similar to Week 26 visit and, if subjects agree, the subjects will return 4 weeks later for a follow-up visit similar to Week 30 visit.

During the course of the study, an independent Data and Safety Monitoring Board (DSMB) will be assembled to periodically review and evaluate accumulated study data for subject safety, study conduct and progress. The DSMB will have the responsibility to make recommendations concerning continuation, modification, or termination of the study.

The approximate blood volume to be collected during the study is 135.5 mL, with a maximum of 26 mL per visit.

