6.4.1.2 Modified Hachinski Ischemic Scale (MHIS)

The MHIS, a tool to identify the possibility of a vascular etiology for the subject's dementia, will be completed by a qualified, trained rater at the screening visit, as described in [Appendix 9](#).

6.4.1.3 *National Institute of Neurological and Communicative Diseases and Stroke/Alzheimer's Disease and Related Disorders Association Criteria for Probable Alzheimer's Disease*

The NINCDS-ADRDA criteria for probable Alzheimer's disease will be reviewed at screening, as described in [Appendix 10](#).

6.4.2 *Apolipoprotein E Genotype Testing*

At baseline, a blood sample will be drawn for APO-E genotype testing. Subjects (or caregiver) will be provided the results of the test at the conclusion of the study, upon request.

To obtain sufficient DNA for APO-E genotyping, a single blood sample of 4 mL will be drawn into the appropriate tube (see the Laboratory Manual for sample acquisition, shipping and labeling instructions).

6.4.3 *Pharmacokinetics*

Plasma samples will be analyzed for levels of SUVN-502 and M1 of SUVN-502 at steady state (Week 4 of treatment) and at Week 26 to gather information on population pharmacokinetics. Plasma samples will be analyzed for levels of donepezil and memantine at screening, Week 4 and at Week 26 to determine compliance with these study treatments.

At Weeks 4 and 26, plasma samples will be collected before study drugs are administered to the subjects. It is recommended, on the day prior to and/or day of visits where pharmacokinetic (PK) sampling is performed, that the date, time and frequency (qd or bid) of SUVN-502, donepezil HCl and memantine HCl administration be noted by the subject or the caregiver to determine the timing of last dose administered. This information will be reviewed during each study visit and entered into the eCRF.

Venous blood samples (approximately 6 mL) will be collected in Li-Heparin vacutainer, and centrifuged within 30 minutes of collection, for 10 min, at 3000 RPM at +4°C to obtain plasma samples. If a refrigerated centrifuge is not available at the site, samples can be centrifuged at ambient temperature. The blood sample should be kept on crushed ice until centrifuged. The plasma should be divided into 4 tubes:

- One tube will be used for plasma levels of SUVN-502 and M1 of SUVN-502.
- One tube will be used for plasma levels of donepezil and memantine.

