7.2.7 Early Termination and Follow-Up Visits

Subjects who discontinue early from the study should, if possible, have an Early Termination visit. This visit should take place as soon as possible after the subject stops taking study drug. The observations and procedures scheduled for Visit 5 (Week 26) should be performed at the Early Termination visit. If the subject agrees, he/she should return for a follow-up visit 4 weeks later. The observations and procedures scheduled for Visit 6 should be performed at the Follow-up visit.

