4.2.2 Visit Windows

Assessments will be classified based on the visit information reflected on the eCRF. Assessments taken outside of protocol allowable windows will be assigned based on the closest scheduled visit. If there are assessments recorded on a day that is equidistant between two visits, the assessments will be attributed to the later visit. The only exception to this rule is for assessments recorded between Baseline and Week 4. Any assessment recorded after the Baseline visit will be mapped to Week 4 even if the day is closer to the Baseline visit. The timetable of visits is given in Section 7.1 in the protocol. Nominal study visits (Weeks relative to Baseline) will be used to summarize data presented by visit.

If subjects have more than one observation for a given time point, the average of the measurements will be used. This rule applies to efficacy data. For safety data, unless otherwise specified, if there is a repeated evaluation, the worst value will be used. If values are equal, the latest repeated (latest) value will be used.

If subjects withdraw early from the study, all study assessments at the early withdrawal visit will be assigned based on the rules described above. That is, they will be assigned to the closest scheduled visit. Data from subjects who discontinue but return after 4 weeks for the follow-up visit will be summarized with the Week 30 visits.

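### SAP 4.9.1 sets no limit on time since the last tablet, so off-drug and missed-dose SUVN-502/M1 samples would be tabulated as troughs

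*SAP*

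**What the plan says.** SAP 4.9.1 describes the PK output: "Concentration data (trough levels) will be summarized for SUVN-502 and M1 of SUVN-502 for each visit by treatment group". The statistics are geometric and arithmetic mean, minimum, maximum, SD and %CV, in the Safety Population. The one filter is that concentrations are "excluded from the analyses if the sample of blood was drawn after the subject received the daily dose of the particular medication".

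Protocol 7.2.7 says of the Early Termination visit: "This visit should take place as soon as possible after the subject stops taking study drug". It gives no maximum delay and calls for all Visit 5 procedures. Protocol 7.2.5 lists the SUVN-502/M1 plasma sample among these, and the Week 26 column of Table 3 also covers early withdrawal. For such subjects SAP 4.2.2 says that "all study assessments at the early withdrawal visit will be assigned based on the rules described above", meaning the closest scheduled visit, with ties going to the later one.

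Protocol 3.1 sets the sampling schedule: "Blood samples for plasma levels of SUVN-502, its metabolite (M1 of SUVN-502), donepezil and memantine will be collected at Weeks 4 and 26". The Week 13 procedures in Protocol 7.2.4 contain no PK sample.

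Protocol 6.4.3 recommends that dose dates and times around PK visits be noted "to determine the timing of last dose administered" and has them entered in the eCRF. SAP 4.9.1 does not use them.

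**The concern.** A trough is the concentration at the end of a dosing interval, here about 24 h after the previous tablet. The SAP filter removes samples taken too soon, after the visit-day dose, but not samples taken too late. Two kinds of late sample are foreseeable. One comes from a subject who has stopped drug and attends an early-termination visit. The other comes from a continuing subject who missed the previous day's tablet. Both pass the filter.

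Evaluating the pharmacokinetics of SUVN-502 given with donepezil and memantine is a stated secondary objective, and these descriptive tables are the only PK analysis that either document sets out. If washout samples are mixed in, the tables understate steady-state exposure and overstate its variability. The distortion would differ between doses if dropout or visit delay did.

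**Working it through.** **The plan's own figure.** SAP 4.9.1 gives none. The sample size serves only for scale: difference 2, SD 6, two-sided 5% and 80% power need 143 per arm by t-test, and 143/0.8 = 179, as stated in SAP 4.10.

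**Step 1: where early-termination samples go.** Target days are 28, 91, 182 and 210. Midpoints are (28+91)/2 = 59.5 and (91+182)/2 = 136.5. Under SAP 4.2.2:
- Days 2-59 map to Week 4.
- Days 60-136 map to Week 13.
- Days 137-195 map to Week 26.

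A Week 13 SUVN-502/M1 value could otherwise arise only from a Week 4 or Week 26 visit badly off schedule.

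**Step 2: what a late SUVN-502 sample contains.** Protocol 1.1.3: "Mean half-life was comparable between the two doses at 13.7 and 12.5 hours, respectively" (50 mg and 100 mg). With first-order decline, the fraction of the 24 h trough at t hours is r = 2^(-(t-24)/half-life).

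| Hours since last tablet | 50 mg (13.7 h) | 100 mg (12.5 h) |
|---|---|---|
| 48 | 29.7% | 26.4% |
| 72 | 8.8% | 7.0% |
| 168 | 0.07% | 0.03% |

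**Step 3: M1.** No half-life is given. One can be inferred from the Day 14/Day 1 exposure ratios in Protocol 1.1.3 (2.1-2.5 at 50 mg, 1.6-1.8 at 100 mg) using R = 1/(1-exp(-24k)). This gives about 17 to 33 h, and residuals of 38-60% at 48 h and 14-36% at 72 h. M1 therefore probably falls more slowly than SUVN-502.

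**Step 4: effect on the Week 26 table.** Assumptions, none from the documents: dropout is spread evenly over Days 2-181 (180 days), every dropout is sampled, all early-termination samples have the same delay, and true troughs are equal across subjects.

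- At 20% dropout, 0.20 × 179 = 35.8 per arm. Week 4 receives 58/180 × 35.8 = 11.5, Week 13 receives 77/180 × 35.8 = 15.3, and Week 26 receives 45/180 × 35.8 = 9.0.
- The early-termination share of the Week 26 table is p = 9.0/(143.2+9.0) = 5.9%.
- The geometric mean is multiplied by r^p. At 72 h this is 0.867 (50 mg) and 0.855 (100 mg), a fall of 13-15%.
- The arithmetic mean is multiplied by (143.2 + 9.0r)/152.2. At 72 h this is about 0.946, a fall of about 5%.
- At 168 h the geometric mean falls 35-38% and the arithmetic mean about 6%.
- At 5% dropout, 8.95 per arm drop out and 2.2 map to Week 26. At 72 h the geometric mean falls about 3% and the arithmetic mean about 1%.

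For M1 at 20% dropout and 72 h, 0.14^0.059 = 0.89 and 0.36^0.059 = 0.94, a fall of about 6-11%.

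**The case against.** **The label may itself restrict the tables.** A sample taken after permanent discontinuation is not a trough in ordinary usage, so a careful analyst might leave it out. But the section states one filter and SAP 4.2.2 states one mapping rule. Following both as written puts the sample in.

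**The Week 13 table depends on a literal reading.** The phrase about each visit can mean each visit with PK sampling, and the closest scheduled visit can mean the closest one at which PK is scheduled. This stands: a reader might infer that the plan certainly yields a Week 13 trough table made up of dropouts, and the documents do not establish that. The alternative reading moves the late samples without removing them. The split falls at (28+182)/2 = Day 105, so Days 105-181 (77 of 180) go to Week 26, about 15 per arm at 20% dropout instead of 9.

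**The percentages rest on assumptions.** This also stands. Twenty percent is the planning ceiling, attendance is asked for only if possible, and the visit should be prompt. A subject who took a tablet the day before gives a valid trough. A reader might infer a large and certain bias; the text supports only a possible one whose size is unknown. Nor does it support saying that the geometric mean could not be computed, because no rule for values below quantification is visible.

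**Redaction.** Parts of SAP 4.6.1 and 4.6.2 and the Evaluable Population definition are blacked out, and a plasma-based rule may lie there. SAP 4.9.1 shows no redaction and refers to no such rule.

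**Consequence.** The tables are descriptive with no test attached, and Protocol 3.2.4 collects the samples for population pharmacokinetics, where dose times would normally be used. This limits the importance of the point but does not correct the tables.

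**Conclusion.** The point holds for the wording of SAP 4.9.1 read with SAP 4.2.2 and Protocol 7.2.7. Off-drug and missed-dose samples are not excluded and would be reported as Week 4 or Week 26 troughs; a Week 13 table follows only from the literal reading. The loss in an individual SUVN-502 sample is large and rests on the stated half-lives plus first-order decline. The effect on the tables is modest to moderate, depends on dropout, attendance and delay, and is much greater for the geometric than the arithmetic mean.

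A reader might infer that efficacy results are compromised. They are not: no efficacy analysis uses these tables. SAP 4.6.2 does use Week 26 concentrations for Evaluable Population inclusion when accountability cannot be determined, but that is a separate rule, and Protocol 8.1.3 limits that population to subjects who complete 26 weeks. The change should be made because it is cheap and serves a stated secondary objective.

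**What to change.** In SAP 4.9.1, summarise as troughs only pre-dose SUVN-502/M1 samples at Weeks 4 and 26 whose last recorded double-blind tablet was taken on the previous day. A time-since-dose window would also serve, if set before unblinding and wide enough for morning dosing and later visit times: a 07:00 tablet followed by a noon visit the next day is already 29 h. List early-termination samples, other samples outside the rule and samples with no last-dose time, with hours since last dose where known, and do not map them to a visit table.

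The cost is a few lines of SAP text and one derived variable from dosing times meant for the eCRF. The trough tables will have a smaller n. Because Protocol 6.4.3 only recommends recording dose times, some genuine troughs will be lost to missing times, and the number cannot be estimated from the documents.
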